## 10.4 RATIONALE FOR SELECTION OF DOSES IN THE STUDY

The starting dose for this study will be 40 mg QD taken for 1 week. A dose of 40 mg BTRX-246040 given QD has been tested and was well-tolerated in two efficacy studies, in male and female patients with MDD (Study NOAC) and male and female patients with AD (Study NOAD). There were no deaths or SAEs with BTRX-246040 administration in either study. In study NOAC, the most common TEAEs that occurred more frequently with BTRX-246040 than placebo were nausea (7/69 [10.1%] vs. 1/65 [1.5%] patients), insomnia (7/69 [10.1%] vs. 0/65 patients) and dizziness (5/69 [7.2%] vs. 0/65 patients). In study NOAD, the frequency of TEAEs reported was similar between the BTRX-246040 and placebo treatment groups. In both studies, most TEAEs were mild or moderate in severity. There were no notable treatment-related clinical laboratory findings or abnormal ECGs. Vital signs were generally within normal ranges, with no notable treatment-related changes reported following 40 mg QD BTRX-246040. In both studies, no increase in suicidal ideation or behavior relative to placebo was detected following BTRX-246040 administration, as assessed by the C-SSRS.

In male healthy volunteer study NOAA, BTRX-246040 was shown to be safe and well-tolerated up to 800 mg given as a single dose and up to 200 mg QD after multiple dosing for 14 days. In general, the observed BTRX-246040 concentration time data in patients with MDD were in a similar range to the concentrations observed in this healthy subject study when the data were compared after normalizing for administered dose. In this study, observed Cmax estimates after dosing 40 mg QD for 14 days ranged from 87.9 to 183 ng/mL (mean=127 ng/mL). The exposure multiple to the lowest convulsive dose in the nonclinical study in dogs is 19X and the exposure multiple to 1/10th the convulsive threshold in dogs is approximately 2X based on the mean Cmax at 40 mg.

The 40 mg dose was well-tolerated in two separate Phase 2 studies (n = 113 male and female patients treated with BTRX-246040) and a trend towards efficacy in MDD was observed although the MDD study did not meet the success criteria of the primary endpoint. For this reason, dose titration from 40 mg to 80 mg QD based on individual patient tolerability will be employed in the current study to further explore the effective dose range. A dose decrease to 40 mg QD will be allowed if the 80 mg QD dose is not tolerated.

## 10.5 SELECTION AND TIMING OF DOSES

BTRX-246040 has only been dosed with a light breakfast in clinical pharmacology studies to date; there are currently no PK data available for BTRX-246040 when dosed in the fasted state. Therefore, in the current study, patients will take the investigational study drug orally at approximately the same time every morning with a light breakfast.

All patients will be instructed to take their first dose of BTRX-246040 or placebo on the day of Visit 2 (baseline) after completing all baseline study procedures. Patients will take their study drug in the clinic with a light snack.

Patients will be instructed to refrain from taking their investigational study drug at home on the morning of Visits 3, 4, 5, and 6. Study drug will be administered with a light snack at the site from the bottle dispensed at the visit.

## 10.6 BLINDING

This is a double-blind study. Patients, site personnel, and the Sponsor will be blinded to treatment.

Emergency unblinding for AEs must be performed through the IWRS. This option may be used ONLY if the patient's well-being requires knowledge of the patient's treatment assignment. All requests resulting in an unblinding event are recorded and reported by the IWRS.

The Investigator should make every effort to contact the medical monitor prior to unblinding a patient's treatment assignment. If an Investigator, site personnel performing the assessments, or patient is unblinded, the patient must be discontinued from the study. In cases where there are ethical reasons to have the patient remain in the study, the Investigator must obtain specific approval from the Sponsor-designated Medical Monitor for the patient to continue in the study.

## 10.7 CONCOMITANT THERAPIES

In general, concomitant medications with primarily CNS activity are not allowed in the study. The Investigator should instruct the patient to notify the study site about any new medications he/she takes and about any significant non-pharmacological therapies administered after the start of the study drug (e.g. acupuncture, hypnosis etc.). All medications, including over the counter medications and supplements, and also significant non-pharmacological therapies, administered after the patient starts treatment with study drug must be listed on the corresponding CRFs.

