Based on data from rat and rabbit reproduction toxicity studies, BTRX-246040 does not pose a significant safety hazard to a developing embryo or fetus. In rats, BTRX-246040 did not cause major malformations or effects on embryo-fetal survival. Slightly reduced fetal growth and an increase in minor fetal anomalies occurred at the maternally toxic dose of 200 mg/kg/day which corresponded to an AUC of 204485 ng.h/mL on Gestation Day 17. The Margin of Safety (MOS) for the AUC at the no-observed- adverse-effect-level (NOAEL) of 75 mg/kg/day relative to the AUC at the 40 mg in study NOAA is 69-fold and 57-fold above the expected AUC at the 80 mg dose. In rabbits, BTRX-246040 did not cause major or minor fetal anomalies or adversely affect embryo-fetal survival. A slight reduction in fetal weights occurred concurrently with significant maternal toxicity (body weight loss and reduced food consumption) at 100 mg/kg/day (AUC – 11381 ng.h/mL). The MOS for the AUC at the NOAEL of 30 mg/kg/day relative to the AUC at the 40 mg dose in study NOAA is 2.5-fold and 0.9-fold at the expected AUC at the 80 mg dose. In general toxicity studies, dose-limiting toxicity was mainly related to dose- and exposure-dependent increases in severity of central nervous system (CNS) effects in rats and dogs including ataxia, tremors (dogs only), and convulsions (dogs only). The lowest maximum drug plasma concentration (Cmax) that produced convulsions in dogs (the most sensitive preclinical species) was 2400 ng/mL (approximately 19-fold above the mean Cmax anticipated with 40 mg QD and 7-fold above the mean Cmax anticipated with 80 mg QD).

The current study will use a starting dose of 40 mg QD for which observed Cmax estimates after dosing for 14 days to healthy male patients in Study NOAA ranged from 87.9 to 183 ng/mL (mean=127 ng/mL). The exposure multiple to the lowest convulsive dose in dogs is 19-fold and the exposure multiple to 1/10th the convulsive threshold in dogs is approximately 2-fold based on the mean Cmax at 40 mg observed in Study NOAA. Since this dose was well-tolerated in two separate Phase 2 studies (n = 113 male and female patients treated with BTRX-246040) in which

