a trend towards efficacy was observed, dose escalation to 80 mg QD based on individual patient tolerability will be employed in the current study to further explore the effective dose range. PK data are available for the dose regimens of 40, 120, and 200 mg QD, but not for 80 mg QD. The mean Cmax on Day 14 of dosing with 120 mg QD to healthy male patients in Study I5J-MC-NOAA (NOAA) was 570 ng/mL. Thus, the mean Cmax and AUC0-24 with steady-state dosing with 80 mg QD is anticipated to be approximately 350 ng/mL and 3550 ng.h/mL, respectively (intermediate between that of 40 mg QD and 120 mg QD).

More information about the known and expected benefits, risks and reasonably anticipated AEs may be found in the Investigator's Brochure (IB).

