10. Have alanine aminotransferase (ALT) or aspartate aminotransferase (AST) levels  $\geq 2x$  upper limit of normal (ULN) or glomerular filtration rate  $\leq 60$  mL/min at Visit 1 (screening).

11. Positive HCV antibody (Ab), hepatitis B surface antigen (HBs Ag), HAV IgM antibody (HAV-Ab [IgM]) or HIV test at Visit 1 (screening).
12. Have nephritic syndrome, end-stage renal disease (and using renal replacement therapy such as hemodialysis or peritoneal dialysis), or a serum creatinine  $\geq 2$  mg/dL ( $\geq 172$   $\mu$ mol/L) at Visit 1 (screening).
13. Have a thyroid-stimulating hormone (TSH), free T4, or total T3 level outside of the established reference range that is deemed clinically significant by the Investigator at Visit 1 (screening). Patients previously diagnosed with hyperthyroidism or hypothyroidism who have been treated with a stable dose of thyroid supplement for at least 3 months prior to Visit 1 (screening) and are clinically and chemically (normal free T4) euthyroid will be allowed to participate in the study.
14. Have any other clinically significant abnormalities (significant would include laboratory deviations requiring acute medical intervention or further medical evaluation) in laboratory results at screening, including clinical chemistries, hematology, and urinalysis, and any clinical information that, in the judgment of the Investigator, should preclude a patient's participation at study entry.
15. Have ECG abnormalities obtained at Visit 1 (screening) or Visit 2 (baseline) that, in the judgment of the Investigator, are clinically significant regarding the patient's participation e.g. QTcF  $> 450$  msec in males,  $> 470$  msec in females, Left Bundle Branch Block, Myocardial Infarction findings with current coronary artery disease.
16. Have a history of substance or alcohol use disorder within 12 months prior to Visit 1 (screening) as defined by DSM-5. Note: Nicotine and caffeine use disorder are not excluded.
17. Have a positive urine drug screen at Visit 1 (screening) or Visit 2 (baseline) that has not been deemed acceptable by the Medical Monitor (see [section 11.4.2](#)).
18. Use of the following concomitant medications (contact the Sponsor-designated medical monitor to determine eligibility when in doubt):

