  - a. psychoactive medication including stimulants, benzodiazepines and anxiolytics, oral antipsychotics, mood stabilizers (carbamazepine, lamotrigine, etc.), lithium, antidepressants and hypnotics/sedatives within 5 half-lives of Visit 2 (baseline).
  - b. proton pump inhibitors within 5 half-lives of Visit 2 (baseline)
  - c. depot antipsychotics, fluoxetine and irreversible monoamine oxidase inhibitors within 4 weeks of Visit 2 (baseline)
19. Are currently taking or have taken within 5 half-lives of Visit 2 (baseline) any medications or supplements that are strong inhibitors or inducers of CYP3A4 (see [Appendix 1](#)).
20. Have a known hypersensitivity to gelatin capsules.
21. Are women who are either pregnant or breastfeeding.
22. Are Investigator site personnel directly affiliated with this study, and/or their immediate families. Immediate family is defined as a spouse, parent, child, or sibling, whether

biological or legally adopted.

23. Are employees of the Sponsor or are employees of any third-party organizations (TPOs) involved in study who require exclusion of their employees.
24. Have participated in a clinical trial or any other type of medical research judged by the Investigator to be scientifically or medically incompatible with this study within 30 days prior to Visit 1 (screening). Contact the Sponsor-designated medical monitor to determine eligibility when in doubt.
25. Have previously completed or withdrawn from this study or any other study investigating BTRX-246040 (previously called LY2940094).
26. Not willing to install and maintain smartphone applications for the digital assessments throughout participation in the study

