## 8.3 DISCONTINUATIONS

### 8.3.1 EARLY DISCONTINUATION

Patients who discontinue from the study early will have end of treatment assessments performed as shown in the Schedule of Assessments, [Table 1](#). Every effort will be made to encourage them to complete all Visit 7 (week 8) assessments and follow-up visit assessments.

If early discontinuation occurs, the primary reason will be determined and reported on the study completion CRF. Reasons for early discontinuation listed in the CRF are: Investigator/Physician decision, patient decision (withdrawal of consent), Sponsor decision, AE(s), unsatisfactory therapeutic effect, and loss to follow-up.

1. Investigator/Physician Decision
  - a. The Investigator/physician decides that the patient should be withdrawn from the study for any reason. For example, the patient is significantly noncompliant with the study drug regimen (see [section 10.8](#); Patients with investigational product compliance  $\leq 70\%$  over any 2-week visit interval)
  - b. After Visit 2 (baseline) the patient is found to have met an exclusionary criterion or not met an entry criterion required for study participation.
  - c. The patient is enrolled in any other clinical trial involving an investigational product or is enrolled in any other type of medical research judged not to be scientifically or medically compatible with this study.

2. Patient Decision

- a. The patient requests to be withdrawn from the study for any reason. If the reason to request withdrawal is an adverse event this should be documented as the primary reason for discontinuation.

3. Sponsor Decision

- a. An Investigator, site personnel performing assessments or patient is unblinded (see [section 10.6](#)).

4. The Sponsor stops the study or stops the patient's participation in the study for medical, safety, regulatory or other reasons consistent with applicable laws, regulations and good clinical practice (GCP).

5. Adverse Event

- a. The patient experiences an AE that would necessitate discontinuation of investigational product. If this decision is made because of an SAE or a clinically significant laboratory value, the investigational product is to be discontinued and appropriate measures are to be taken (see [item 5. d.](#) below). The Sponsor or its Medical Monitor designee is to be alerted immediately (see [section 11.3](#)).

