- b. Discontinuation should be considered by the Investigator after consultation with the Sponsor or its Medical Monitor designee when a patient has the following abnormal liver tests:
  - i. ALT or AST > 8 x ULN
  - ii. ALT or AST > 5 x ULN for more than 2 consecutive weeks
  - iii. ALT or AST > 3 x ULN and total bilirubin level > 2 x ULN
  - iv. ALT or AST > 3 x ULN and prothrombin time > 1.5 x ULN
  - v. ALT or AST > 3 x ULN with the appearance of fatigue, nausea, vomiting, right upper-quadrant pain or tenderness, fever, rash, and/or eosinophilia (>5%).
- c. If the patient is thought to be at risk of harm to him/herself or others at any time during the study, a further psychiatric assessment by the Investigator must be conducted. Patients must be discontinued from study participation if they:
  - i. are assessed as homicidal
  - ii. are actively suicidal (any suicidal ideation with intent or specific plan or any suicide attempt)
  - iii. are at serious suicidal risk as assessed by the C-SSRS (score of "YES" on item 4 or 5)
  - iv. score  $\geq 5$  on item 10 of either the computer- or Investigator-administered MADRS item 10.

The Investigator must assure that these patients receive the appropriate psychiatric care and follow-up.

- d. Any patient who is discontinued from investigational product due to AEs or clinically significant laboratory abnormalities will be followed until resolution or clinical stabilization.
  - e. The Investigator remains responsible for following, through an appropriate healthcare option, AEs that caused the patient to discontinue study drug.
6. Unsatisfactory Therapeutic Effect
- a. If the patient requires treatment with another therapeutic agent for MDD, discontinuation from the study will occur prior to introduction of the new agent.
7. Loss to Follow-Up
- a. For patients who are lost to follow-up, all steps performed to contact them (dates of telephone calls, registered letters, etc.) will be reported in the source documents. The Investigators are required to make at least two attempts to contact the patient for a follow-up safety visit.
8. Pregnancy
- a. Study drug treatment will be discontinued for female patients who become pregnant during study. See [section 11.3.3](#) for additional information.

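### Strong CYP3A4 inhibitors and inducers are barred at entry, but nothing explicitly continues the bar during treatment; the main gap is prolonged inhibitor use at 80 mg once daily

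*Protocol*

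**What the plan says.** **At entry.** Protocol section 8.2, exclusion 19, applies to patients who "Are currently taking or have taken within 5 half-lives of Visit 2 (baseline) any medications or supplements that are strong inhibitors or inducers" of CYP3A4. Appendix 1 lists the drugs and restates the criterion. Exclusion 18b similarly bars "proton pump inhibitors within 5 half-lives of Visit 2 (baseline"). Under exclusion 18, sites are to "contact the Sponsor-designated medical monitor to determine eligibility when in doubt".

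**During treatment.** Section 10.7 is the rule on concomitant therapy: "In general, concomitant medications with primarily CNS activity are not allowed in the study". Beyond that, patients are told to inform the site of new medications, and these are entered on the CRF.

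**Discontinuation.** Section 8.3.1 item 1b, under Investigator decision, covers the case where "After Visit 2 (baseline) the patient is found to have met an exclusionary criterion". Item 6a concerns antidepressant rescue: "If the patient requires treatment with another therapeutic agent for MDD, discontinuation from the study will occur prior to introduction of the new agent".

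**Analysis sets.** SAP section 5.4 gives receipt of prohibited medication as an example of a major deviation that may remove a patient from the per-protocol set. It does not say which medications are meant.

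**Exposure.** Section 5 states that the lowest Cmax producing "convulsions in dogs (the most sensitive preclinical species) was 2400 ng/mL", about 19-fold above the mean at 40 mg and 7-fold above that anticipated at 80 mg. It adds: "PK data are available for the dose regimens of 40, 120, and 200 mg QD, but not for 80 mg QD". Section 10.1 allows one reduction to 40 mg, only through Visit 4 (week 2).

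**The concern.** The sponsor judged strong CYP3A4 agents unacceptable at Visit 2, when the patient is about to take 40 mg. Nothing in the text gives a reason for them to become acceptable a week later at 80 mg. Yet a site that follows 10.7 literally could let a patient start a non-CNS strong inhibitor and do no more than record it.

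At stake is exposure above what was planned, at a dose with no PK data, for a compound whose dose-limiting animal toxicity includes convulsions and whose protocol excludes patients at raised seizure risk. After Visit 4 the dose can no longer be reduced. For 6 of the 7 weeks at 80 mg, the remaining responses are to stop the new drug or to stop study drug.

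**Working it through.** **1. Does any text continue the bar?**

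- Exclusion 19 has one dated anchor, Visit 2. Its present-tense wording about current use is undated, so item 1b of 8.3.1 could be read as reaching a later start. Item 1b more naturally covers ineligibility discovered late.
- Exclusion 8 (psychotherapy) is expressly extended through the acute phase. Exclusions 18 and 19 carry no such words.
- Section 10.7 is limited to primarily CNS-active drugs. That already covers some Appendix 1 entries, such as nefazodone, carbamazepine and phenytoin. It does not cover clarithromycin, itraconazole, ketoconazole or grapefruit juice. Juice is also not plainly a medication or supplement that a patient would report.
- The Medical Monitor contact in exclusion 18 concerns eligibility, not a later start.
- SAP 5.4 operates after the fact and points to no on-treatment list.

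The bar is therefore explicit at entry and at best implied afterwards.

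**2. The plan's own margins.** Inputs are from protocol section 5: mean Cmax 127 ng/mL (40 mg) and 570 ng/mL (120 mg), anticipated 350 ng/mL (80 mg), dog convulsive Cmax 2400 ng/mL.

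- 40 mg: 2400/127 = 18.9 (stated 19)
- 80 mg: 2400/350 = 6.86 (stated 7)
- Midpoint of 127 and 570: 348.5 (stated approximately 350)

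All three reproduce.

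**3. What an interaction could do at 80 mg.** The fold rise F is an assumption. Appendix 1's 5-fold cut-off classifies inhibitors by their effect on AUC of a substrate; it is used here only as an upper assumption. At full steady state:

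- F = 1: 350 ng/mL, margin 6.9
- F = 2: 700 ng/mL, margin 3.4
- F = 5: 1750 ng/mL, margin 1.4

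The drug is slow to accumulate (section 5 gives a half-life h of 66 to 96 hours), so short courses reach less. Assume one compartment, reduced clearance only, half-life lengthened F-fold, and Cmax scaling with average level. Then after t hours of inhibitor:

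Level = 350 × [1 + (F − 1) × (1 − 2^(−t/(F × h)))]

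| Duration | F = 2, ng/mL | Lowest margin | F = 5, ng/mL | Lowest margin |
|---|---|---|---|---|
| 7 days | 509–555 | 2400/555 = 4.32 | 652–766 | 2400/766 = 3.13 |
| 14 days | 596–640 | 2400/640 = 3.75 | 888–1059 | 2400/1059 = 2.27 |
| 42 days | 691–698 | 2400/698 = 3.44 | 1423–1581 | 2400/1581 = 1.52 |

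The upper end of each range uses h = 66 hours, the lower end h = 96 hours. At 42 days and F = 5 the lower end gives 2400/1423 = 1.69. All levels start from the mean. At 40 mg the highest individual Cmax was 183/127 = 1.44 times the mean, so some patients would start with less margin.

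**4. Human context.** Section 10.4 reports that healthy men tolerated 200 mg once daily for 14 days. Its Cmax is not given. Scaling 570 in proportion gives 570 × 200/120 = 950 ng/mL. A power fit through 127 and 570 has exponent ln(570/127)/ln(3) = 1.37 and gives about 1150 ng/mL. On this model a 7-day course at 5-fold (at most 766) stays within tested repeat-dose exposure, and a 14-day course (at most 1059) is close to it. Six weeks (1423 or more) exceeds it.

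**5. Monitoring interval.** From Visit 4 the visits fall on days 15, 29, 43 and 57, so 14 days apart. A 7-day course can start and finish between reviews.

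**6. Inducers.** A fall of 80% would take 350 to 70 ng/mL, below the 127 at 40 mg. That would be a loss of exposure, not a convulsion risk.

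**The case against.** The case for leaving the text alone has several parts.

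- **The bar may already be implied.** Exclusion 19's present tense, item 1b and the reference to prohibited medication in SAP 5.4 can be read together as a continuing bar. This stands as a reasonable reading, but a site should not have to assemble a safety rule from three places.
- **Few drugs and patients are involved.** CNS-active agents fall under 10.7, antidepressants also under item 6a, and patients positive for HIV or hepatitis C are excluded. About 50 patients take active drug for 8 weeks. This stands and limits the point.
- **No harm is shown.** Neither document states that BTRX-246040 is a CYP3A4 substrate, and the Investigator's Brochure, which may hold interaction guidance, is not among them. This stands in full: the interaction could be nil.
- **Short courses look tolerable.** The arithmetic above agrees, which is why prolonged use is the main concern.
- **Safeguards exist.** Patients must report new medications; concomitant therapy, adverse events and neurological status are reviewed at every visit; the Medical Monitor reviews blinded safety data; the Investigator may withdraw a patient for any reason. These reduce the risk. None requires the Medical Monitor to be contacted when a strong inhibitor is needed or started.

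A reader might go further and infer that an ordinary antibiotic course would bring patients near the convulsive level. The documents do not support that: the 1.4 margin needs an undocumented 5-fold interaction held to full steady state, which the model does not reach even in six weeks.

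**Conclusion.** The gap is real and worth closing, as a low-frequency, precautionary safety point. It concerns mainly prolonged use of non-CNS strong inhibitors at 80 mg once daily. As written, 10.7 permits an exposure that the sponsor ruled out at entry.

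Its size is unknown and possibly nil. With no interaction the margin stays at 6.9. With an assumed 5-fold interaction it falls to between 3.1 and 3.7 after 7 days (2400/766 and 2400/652) and to between 1.5 and 1.7 after six weeks. These figures rest on the one-compartment assumptions stated, on mean rather than individual Cmax, and on an anticipated rather than observed 350 ng/mL.

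Three wider readings should be resisted:

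- **Threat to the primary result.** Few patients would be affected in either arm, and nothing here changes the full-analysis-set comparison, the sample size or the power.
- **Proton pump inhibitors as a hazard.** Exclusion 18b has the same timing gap, more plainly since it is worded only relative to Visit 2, but the documents give no direction or size of harm. Only consistency argues for including them.
- **Sites left without any control.** Notification and review are in place; what is missing is an explicit prohibition and a required Medical Monitor contact.

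**What to change.** Keep the existing sentence in protocol section 10.7 and add:

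*Strong CYP3A4 inhibitors and inducers (strong columns of Appendix 1) remain prohibited from Visit 2 through the last dose of study drug. If one is needed or has been started, the site contacts the Medical Monitor promptly to decide whether study drug is stopped. Necessary treatment must not be withheld.*

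In SAP section 5.4, define prohibited medications by reference to protocol section 10.7. Proton pump inhibitors may be added to the sentence to match exclusion 18b, without a safety claim.

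The cost is a short addition to the protocol, one line in the SAP and one new contact step for sites. A few patients may stop study drug or leave the per-protocol set. The change does not by itself detect a course started by an outside prescriber between visits; that still depends on the patient telling the site, as 10.7 already asks. Telling patients that grapefruit juice is on the list would help, since they may not think to report it.
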